7.4.1.1.1 Carfilzomib: Guidelines for Hematologic Toxicity

Guidelines for carfilzomib dose modification in the event of thrombocytopenia and neutropenia are summarized in [Table 7-2](#).

Table 7-2. Carfilzomib Modification Guidelines for Thrombocytopenia and Neutropenia

Hematologic toxicity	Recommended Action	
Thrombocytopenia		
When platelets fall to < 30 x 10 ⁹ /L and for each subsequent drop to < 30 x 10 ⁹ /L	If platelets 10 to 30 x 10 ⁹ /L without evidence of bleeding	
 hold restart at previous dose when platelets > 30 x 10⁹/L
	If evidence of bleeding or platelets < 10 x 10 ⁹ /L	
 hold restart at 1 dose decrement when platelets

> 30 x 10 ⁹ /L and bleeding is controlled		
Neutropenia		
When ANC falls to < 0.75 x 10 ⁹ /L and for each subsequent drop to < 0.75 x 10 ⁹ /L	If ANC 0.5 to 0.75 x 10 ⁹ /L	continue at full dose
	If ANC < 0.5 x 10 ⁹ /L	
• hold dose• resume at 1 dose decrement when ANC ≥ 0.5 x 10⁹/L

ANC = absolute neutrophil count.

7.4.1.1.2 Carfilzomib: Guidelines for Nonhematologic Toxicity

Guidelines for dose modification in the event of nonhematologic toxicities are summarized in [Table 7-3](#).

Table 7-3. Carfilzomib Modification Guidelines for Nonhematologic Toxicities

Symptom/Sign/Investigation	Recommended Action
Renal Dysfunction^a:	
CrCl \geq 15 mL/min	Full dose
CrCl < 15 mL/min (NCI-CTCAE grade 4)	Hold dose and monitor renal function. If attributable to carfilzomib, resume when renal function has recovered to within 25% of baseline; re-start at 1 dose level reduction. If not attributable to carfilzomib, dosing may be resumed at the discretion of the physician. If dialysis required, use the maximal dose of 20 mg/m ² and administer carfilzomib after dialysis.
Chronic dialysis stable for \geq 30 days	Dose may be re-escalated up to full dose as clinically tolerated
Hepatic Dysfunction and Related Investigations	
Mild to moderate liver dysfunction: defined as 2 consecutive values, at least 28 days apart, of: (1) total bilirubin (> 33% direct) > 1x ULN to < 3x ULN OR (2) an elevation of AST and/or ALT with normal bilirubin	25% dose reduction. Dose may be re-escalated if liver function tests return to normal and drug-induced hepatotoxicity is excluded.
Grade 3 elevation in ALT and/or AST (> 5x ULN)	Hold carfilzomib until resolution to baseline. Monitor any abnormality weekly. Resume carfilzomib with a 25% dose reduction if drug-induced hepatotoxicity is excluded.
Grade 3 elevation in total bilirubin	Hold carfilzomib until resolution to baseline. Monitor total bilirubin and direct bilirubin weekly. Upon resolution of total bilirubin to normal, resume carfilzomib dosing with a 25% dose reduction if drug-induced hepatotoxicity is excluded.
Drug-induced hepatotoxicity (attributable to carfilzomib)	Discontinue carfilzomib

Page 1 of 4

Footnotes defined on last page of the table

Table 7-3. Carfilzomib Modification Guidelines for Nonhematologic Toxicities

Symptom/Sign/Investigation	Recommended Action
Other Nonhematologic Toxicities	
Tumor lysis syndrome: 3 or more of the following: increase in creatinine of $\geq 50\%$ from baseline increase in uric acid of $\geq 50\%$ from baseline increase in phosphate of $\geq 50\%$ from baseline increase in potassium of $\geq 30\%$ from baseline decrease in calcium from baseline OR increase in LDH of ≥ 2 -fold from baseline	Hold carfilzomib until all abnormalities in serum chemistries have resolved; resume at full dose.
Congestive heart failure	Any subject with congestive heart failure, whether or not drug-related, must have the dose held until resolution or return to baseline. Appropriate medical management should be initiated and continued as clinically indicated. If no resolution after 4 weeks, carfilzomib will be permanently discontinued.
< Grade 3	Once congestive heart failure resolves or returns to baseline, resume at full dose.
\geq Grade 3	Once congestive heart failure resolves or returns to baseline, treatment may continue at 1 dose level reduction.
Infection (grade 3 or 4)	Hold carfilzomib. Once infection is controlled and the subject is without infection-related symptoms, and if ANC $> 1.0 \times 10^9/L$, resume at full dose. If ANC $< 1.0 \times 10^9/L$, follow hematologic toxicities dose reduction guidelines.
Hepatitis B reactivation	Hold carfilzomib until infection is adequately controlled (see Section 7.1.4.7 for guidance on Hepatitis B virus reactivation prophylaxis).
Neuropathy (grade 2 with emergent pain, or grade 3)	Hold carfilzomib until resolved to \leq grade 2 without pain; then resume at 1 dose decrement.
Neuropathy (grade 4)	Permanently discontinue carfilzomib.
Dyspnea (grade ≥ 2)	Hold carfilzomib until resolution to grade 1 or baseline, then resume at 1 dose decrement. Investigate cause and record findings. If caused by another adverse event listed in this table, follow recommendations for that adverse event.

Footnotes defined on last page of the table

Table 7-3. Carfilzomib Modification Guidelines for Nonhematologic Toxicities

Symptom/Sign/Investigation	Recommended Action
Hypertension (SBP > 140 and/or DBP > 90, measured per Section 12.10)	
< Grade 3	Continue at same dose and initiate appropriate treatment to control hypertension (see Section 12.10 for link to guidance).
≥ Grade 3	Hold carfilzomib until resolution to normal or baseline. Initiate appropriate antihypertensive therapy prior to resuming carfilzomib at 1 dose decrement.
Pulmonary toxicity: Non-infectious interstitial lung disease, acute respiratory failure, ARDS (≥ grade 3)	Hold carfilzomib until resolution to grade 1 or baseline and restart at 1 dose decrement.
Pulmonary hypertension (grade ≥ 3)	Hold carfilzomib until resolution to grade 1 or baseline and restart at 1 dose decrement
Posterior reversible encephalopathy syndrome: Headaches, altered mental status, seizures, visual loss, and hypertension	If PRES is suspected, hold carfilzomib. Consider evaluation with neuroradiological imaging, specifically MRI, for onset of visual or neurological symptoms suggestive of PRES. If PRES is confirmed, permanently discontinue carfilzomib. If the diagnosis of PRES is excluded, carfilzomib administration may resume at same dose, if clinically appropriate.
Progressive multifocal leukoencephalopathy	Patients should be monitored for any new or worsening neurologic, cognitive or behavioral signs, or symptoms that may be suggestive of PML as part of the differential diagnosis of CNS disorders. If PML is suspected, withhold administration of carfilzomib; patients should be promptly referred to a specialist and appropriate diagnostic testing should be initiated. Discontinue carfilzomib if PML diagnosis is confirmed.
Thrombotic microangiopathy: Fever, microangiopathic hemolytic anemia, renal failure, thrombocytopenia, neurological manifestations	If the diagnosis is suspected, hold carfilzomib and manage per standard of care including plasma exchange as clinically appropriate. If TMA is confirmed, permanently discontinue carfilzomib. If the diagnosis is excluded, carfilzomib can be restarted
Venous thrombosis (≥ grade 3)	Hold carfilzomib and adjust anticoagulation regimen; resume at full dose once anticoagulation has been optimized per treating investigator's discretion.
Any other drug-related nonhematologic toxicity ≥ grade 3 ^b	For carfilzomib attribution, hold dose. Resume at 1 dose decrement when toxicity has resolved to grade 1 or less or to baseline grade.

Page 3 of 4

ALT = alanine aminotransferase; ANC = absolute neutrophil count; ARDS = acute respiratory distress syndrome; AST = aspartate aminotransferase; CNS = central nervous system; CrCl = creatinine clearance; DBP = diastolic blood pressure; KRd = carfilzomib in combination with lenalidomide and dexamethasone; LDH = lactate dehydrogenase; MRI = magnetic resonance imaging; NCI-CTCAE = National Cancer Institute-Common Terminology Criteria for Adverse Events; PML = Progressive multifocal leukoencephalopathy; PRES = Posterior Reversible Encephalopathy Syndrome; SBP = systolic blood pressure; TMA = thrombotic microangiopathy; ULN = upper limit of normal.

Table 7-3. Carfilzomib Modification Guidelines for Nonhematologic Toxicities

Page 4 of 4

^a For a rapid fall from baseline in CrCl or an absolute fall of ≥ 60 mL/min, contact the medical monitor.

^b In the event of a possible drug-related nonhematologic toxicity, the investigator should, to the best of his/her ability, assess its relationship to pomalidomide (P), carfilzomib (K), dexamethasone (d), or the combination of KPd to the extent possible.

7.4.1.1.3 Conditions Not Requiring Carfilzomib Dose Reduction

Carfilzomib do not need to be held in the following cases:

- grade 3 nausea, vomiting, or diarrhea (that responds within 7 days to adequate treatment of antiemetics and/or antidiarrheal agents)
- grade 3 dexamethasone-related hyperglycemia
- isolated grade 3 γ -glutamyl transferase elevation
- grade 3 fatigue (unless persisting for > 7 days)
- alopecia
- hypogammaglobulinemia

7.4.1.2 Non-Amgen Investigational Product: Pomalidomide

Dose reduction levels of pomalidomide for toxicity management of individual subjects are provided in [Table 7-4](#).

Table 7-4. Dose Decrements for Pomalidomide

Nominal Dose ^a	Reduced Pomalidomide Doses (mg/m ²)		
	Dose -1	Dose -2	Dose -3
4 mg	3 mg	2 mg	1 mg

Pomalidomide will be discontinued, temporarily delayed, or dosage temporarily reduced, in the event of a treatment-related toxicity that, in the opinion of the investigator, warrants the discontinuation, temporary delay or dose reduction as indicated in [Table 7-5](#) and [Table 7-6](#).

Table 7-5. Pomalidomide Modification Guidelines for Thrombocytopenia and Neutropenia

	Recommended Action
	Pomalidomide
Neutropenia	
ANC < 500 per mL or ANC < 1000 per μ L with fever $\geq 38.5^{\circ}\text{C}$	Interrupt pomalidomide treatment, follow complete blood count (CBC) weekly, administer myeloid growth factor

Page 1 of 2

Footnotes defined on last page of the table

Table 7-5. Pomalidomide Modification Guidelines for Thrombocytopenia and Neutropenia

	Recommended Action
	Pomalidomide
Neutropenia (continued)	
ANC return to ≥ 500 per μL	Resume pomalidomide at 3 mg daily
For each additional drop < 500 per μL	Interrupt pomalidomide treatment
Return to ≥ 500 per μL	Resume pomalidomide at 1 mg less than the previous dose
Thrombocytopenia	
Platelets $< 25\,000$ per μL	Interrupt pomalidomide treatment, follow CBC weekly
Platelets return to $> 50\,000$ per μL	Resume pomalidomide at 3 mg daily
For each additional drop $< 25\,000$ per μL	Interrupt pomalidomide treatment
Return to $\geq 50\,000$ per mCL	Resume pomalidomide at 1 mg less than the previous dose

Page 2 of 2

ANC = absolute neutrophil count; CBC = complete blood count

Table 7-6. Pomalidomide Modification Guidelines for Nonhematologic Toxicities

Symptom/Sign/Investigation	Recommended Action
	Pomalidomide
Rash = grade 3	Interrupt pomalidomide. Decrease by one dose level when dosing is resumed at next cycle (rash must be resolved or improved to \leq grade 1 before dose resumption).
Rash = grade 4 or blistering (including angioedema, anaphylactic reactions, exfoliative or bullous rash or if Stevens-Johnson Syndrome (SJS), Toxic Epidermal Necrolysis (TEN), or Drug Reaction with Eosinophilia and Systemic Symptoms (DRESS) is suspected.	Permanently discontinue study treatment
Venous Thromboembolic events (VTE) \geq grade 3	Interrupt dose and initiate anticoagulation treatment. Maintain dose levels when dosing resumed at next cycle at discretion of treating physicians.
Other \geq grade 3 pomalidomide-related adverse events	Interrupt pomalidomide. If dose reduction is appropriate, interrupt pomalidomide for the remainder of the cycle. Start the reduced dose on day 1 of the next cycle. Adverse event should be resolved or improved to \leq grade 2 before restarting treatment.

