7.1.1.2 Pomalidomide

7.1.1.2.1 Dosage Formulation

Pomalidomide will be manufactured and packaged by Celgene.

Pomalidomide is initially supplied as a 4-mg capsule, and supplied as a 3 mg, 2 mg, or 1 mg capsule if dose modification is required (refer to Pomalyst[®] Prescribing Information or Imnovid[®] SmPC for more details).

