7.1.1.2.2 Dosage, Administration, and Schedule

Pomalidomide dose will be 4 mg per day orally on days 1 to 21 of each cycle until progression.

The planned dose (mg), dose administered (mg), start date, stop date, reason for dose change/withheld, reason for dose delay, are to be recorded on each subject's eCRF.

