7.4 Dose Modification

7.4.1 Dosage Adjustments, Delays, Rules for Withholding or Restarting, Permanent Discontinuation

7.4.1.1 Amgen Investigational Product: Carfilzomib

Carfilzomib will be discontinued, temporarily delayed, or dosage temporarily reduced, in the event of a treatment-related toxicity that, in the opinion of the investigator, warrants the discontinuation, temporary delay or dose reduction as indicated in [Table 7-2](#) and [Table 7-3](#) (refer to [Table 7-5](#) and [Table 7-6](#) for KPd pomalidomide dosage adjustments).

Dose reduction levels of carfilzomib for toxicity management of individual subjects are provided in [Table 7-1](#). Subjects who require a dose level reduction and tolerate the reduced dose for 1 full cycle may at the discretion of the treating physician increase the dose to a prior dose starting with the next cycle except when the dose reduction is due to: pulmonary hypertension, pulmonary toxicity, grade 3 or worse cardiac failure, or drug-induced hepatotoxicity.

Table 7-1. Dose Decrements for Carfilzomib

Nominal Dose (mg/m ²)	Reduced Carfilzomib Doses (mg/m ²)			
	Dose -1	Dose -2	Dose -3	Dose -4
20 ^{a, b}	15	11	Discontinue	-
56	45	36	27	20

^a If dose reduction of carfilzomib is required on cycle 1 day 1, the investigator should contact the medical monitor to discuss the situation before any additional doses of carfilzomib are administered.

^b For subjects with baseline chronic hepatic impairment (mild, moderate), reduce the starting and subsequent doses of carfilzomib by 25% (ie, 15 mg/m² day 1 of cycle 1 and 42 mg/m² on day 8 of cycle 1 and thereafter).

The subject will be considered on protocol treatment while receiving carfilzomib or pomalidomide.

If day 1 of a cycle is delayed, all subsequent doses within the cycle and day 1 of subsequent cycles should be adjusted accordingly to maintain the 28-day cycle duration. However, if a within-cycle dose is delayed, then the dates of the subsequent within-cycle doses should not be adjusted. For within-cycle doses, if administration does not commence within the allowable window of the scheduled administration date, then the dose will be considered a missed dose. Administration may resume at the next planned dosing date. A missed dose will not be made up. There should be a minimum of 5 days between carfilzomib doses.

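### Table 7-5 sets the first afebrile pomalidomide neutropenia hold per mL instead of per μL, 1000 times below the table's own resume and re-hold thresholds

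*Protocol*

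**What the plan says.** The first neutropenia row of Protocol Table 7-5 reads "ANC < 500 per mL or ANC < 1000 per" μL, the second limb applying with fever of at least 38.5°C. The action attached to the row is "Interrupt pomalidomide treatment, follow complete blood count (CBC) weekly, administer myeloid growth factor".

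The other three neutropenia rows all use microlitres. Pomalidomide resumes at 3 mg daily once the ANC is back to at least 500 per μL. The re-hold row reads "For each additional drop < 500 per" μL. The last row resumes treatment, 1 mg lower, at 500 per μL or more.

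For carfilzomib, Table 7-2 (Section 7.4.1.1.1) states its hold in SI units: "If ANC < 0.5 x 10"^9/L, hold and resume one dose level lower.

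**The concern.** This row is the entry point to the pomalidomide neutropenia rules; every later neutropenia row presupposes that a first hold has happened. If its threshold is 1000 times too low, severe neutropenia without fever does not set the sequence going.

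Table 7-2 does not close the gap, because it governs carfilzomib only, and a patient can be on pomalidomide without carfilzomib: "The subject will be considered on protocol treatment while receiving carfilzomib or pomalidomide". From cycle 3 the Schedule of Activities (Table 2-1) has hematology on day 1 of each cycle only, so this row is also what would move a neutropenic patient to weekly counts.

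**Working it through.** **Inputs**
- First hold without fever, Table 7-5: ANC < 500 per mL.
- First hold with fever of at least 38.5°C, same cell: ANC < 1000 per μL.
- Resume, re-hold and second resume, Table 7-5: 500 per μL in each.
- Carfilzomib hold, Table 7-2: ANC < 0.5 x 10^9/L.

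**Conversion** (1 mL = 1000 μL; 1 L = 10^6 μL)
- As written: 500 per mL = 500 / 1000 = 0.5 per μL = 0.0005 x 10^9/L.
- Other Table 7-5 rows: 500 per μL = 500 x 10^6 per L = 0.5 x 10^9/L.
- Table 7-2: 0.5 x 10^9/L = 500 per μL, the same level.
- Ratio: 0.5 / 0.0005 = 1000.

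**Literal application to a first ANC of 300 per μL (0.3 x 10^9/L)**

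| Situation | Test as written | Test with μL |
|---|---|---|
| No fever | 0.3 < 0.0005: false, no hold | 0.3 < 0.5: true, hold |
| Fever of at least 38.5°C | 0.3 < 1.0: true, hold | 0.3 < 1.0: true, hold |

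The gap is therefore confined to a first episode without that fever, for ANC from 0.0005 x 10^9/L up to just below 0.5 x 10^9/L. The same count of 300 per μL would meet the re-hold row on a later drop. The re-hold row speaks of each additional drop below 500 per μL, which makes sense only if the first drop was judged against the same figure.

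**Unit tally in Table 7-5.** Of nine thresholds, seven are per μL, one is per mL and one is per mCL. The last is an odd spelling of microlitre and does not change the value. The per-mL entry is the only one that changes the meaning, and nothing elsewhere in the protocol supports it.

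**The case against.** The strongest reply is that this may not be an error in the protocol at all. A PDF reader can turn μL into mL by misreading one character, or mcL into mL by dropping one. Stray characters do occur elsewhere in the text, for example an extra letter I in the MRD[-]CR endpoint name in Protocol Section 10.4.2.2. This stands: a reading fault cannot be excluded from the text alone, so the source page has to be checked first.

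The second reply is that the table corrects itself. The same cell goes on in μL, the next three rows use 500 per μL, and no clinician would hold at 0.5 cells per μL and resume at 500. The tables are guidelines applied in the investigator's judgment. Table 2-1 requires laboratory results to be reviewed before dosing. Section 7.1.1.2.1 points to the product label "if dose modification is required (refer to Pomalyst", and Section 7.1.4.8 permits growth factor when clinically indicated. This also stands, and it is why the risk is rated low. It does not make the cell correct: a dose-hold threshold in the treatment rules should not depend on the reader repairing it.

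Three stronger readings are tempting, and the documents do not support them:
- *That patients went without a needed hold.* Nothing in the protocol or SAP shows that any site applied the literal value.
- *That efficacy results are compromised.* The primary ORR analysis uses the Safety Analysis Set (SAP Sections 6.2 and 9.5), whose membership does not depend on dose holds. The per-protocol set (SAP Section 6.5) does exclude patients whose pomalidomide was not withheld as required (code 508), so a literal reading could blur who counts as a deviator in those sensitivity analyses. With the intended value so plain, any effect is probably small or nil.
- *That units are unreliable throughout the section.* The Table 7-4 header, "Reduced Pomalidomide Doses (mg/m"²), sits over doses given in plain mg, and Section 7.1.1.2.2 fixes a flat daily dose of 4 mg. That header misleads no one and is weak evidence about the origin of the per-mL entry.

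**Conclusion.** The first limb of the first neutropenia row in Table 7-5 is wrong as written, by a factor of 1000: 0.0005 x 10^9/L where 0.5 x 10^9/L is evidently meant. Taken literally, it removes the pomalidomide hold, weekly counts and growth factor for a first severe neutropenia without fever. It matters because it is an operative safety threshold; the practical risk is low for the reasons given above. Sample size and the primary analysis are not affected.

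The conclusion assumes that the source page carries the same unit. If it reads μL or mcL, the point falls away.

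**What to change.** Check the source page of Table 7-5. If it reads mL, change the first neutropenia threshold to ANC < 500 per μL and tell sites in the next routine clarification.

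The cost is one unit in one cell and one line to sites. No special letter is needed, and no design or analysis element changes. Tidying mCL to μL in the last platelet row, and mg/m² to mg in the Table 7-4 header, is optional editorial work that could be done at the same time.

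### Table 7-5's fixed 3 mg pomalidomide restart lowers the dose only from 4 mg, so a subject already at 3 mg with a first non-bleeding platelet drop to 10 to < 25 x 10^9/L restarts with neither pomalidomide nor carfilzomib reduced for that event

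*Protocol*

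**What the plan says.** **Pomalidomide (Protocol 7.4.1.2, Table 7-5).** Neutropenia and thrombocytopenia have separate blocks. In each block the first-episode row ends with "Resume pomalidomide at 3 mg daily", whatever the dose before the interruption. For later drops of the same type the rule is relative: "Resume pomalidomide at 1 mg less than the previous dose". The platelet trigger is below 25 000 per µL, with a weekly blood count and restart above 50 000 per µL. The neutropenia block also directs sites to "administer myeloid growth factor".

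**Carfilzomib (7.4.1.1.1, Table 7-2).** For platelets of 10 to 30 x 10^9/L without bleeding, carfilzomib is held and the instruction is "restart at previous dose when platelets" exceed 30 x 10^9/L. One dose level is taken off only if there is bleeding or platelets are below 10 x 10^9/L. For ANC below 0.5 x 10^9/L the instruction is "resume at 1 dose decrement when ANC" recovers. For ANC 0.5 to 0.75 x 10^9/L it is "continue at full dose".

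**Ways to be at 3 mg before a first platelet drop.** These are an earlier neutropenia (Table 7-5), a grade 3 rash (Table 7-6: "Decrease by one dose level when dosing is resumed at next cycle"), or another grade 3 or higher pomalidomide-related event for which a reduction is judged appropriate (Table 7-6). Section 7.1.1.2.3 also recommends a 3 mg start in Child-Pugh A or B.

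**The concern.** The first-episode rows assume the subject is still at 4 mg, but the protocol's own rules can bring a subject to 3 mg or less beforehand. The most direct route needs only the two cytopenias that Table 7-5 itself covers: neutropenia first, thrombocytopenia second.

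This matters most where Table 7-2 does not reduce carfilzomib either. In that platelet band the pomalidomide step is the only dose reduction in the two tables, and the fixed 3 mg removes it for anyone at 3 mg or below. What is at stake is the dosing instruction after a severe thrombocytopenia, not an efficacy analysis.

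**Working it through.** The plan states no figure on this point, so there is none to reproduce. The check applies the two tables together.

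**1. The platelet band.** 25 000 per µL = 25 x 10^9/L, and 50 000 per µL = 50 x 10^9/L. Pomalidomide is interrupted below 25. Carfilzomib is held without a decrement at 10 to 30 if there is no bleeding. The overlap is 10 to < 25 x 10^9/L, non-bleeding.

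**2. Pomalidomide at a first platelet episode.** Change in daily dose = 3 mg − previous dose. Course dose = 21 days x daily dose.

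| Previous dose | Restart in Table 7-5 | Course dose | Change | Restart under a relative 1 mg step |
|---|---|---|---|---|
| 4 mg | 3 mg | 84 to 63 mg | −25% | 3 mg |
| 3 mg | 3 mg | 63 to 63 mg | 0% | 2 mg |
| 2 mg | 3 mg (literal) | 42 to 63 mg | +50% | 1 mg |

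Paths from 4 mg:
- neutropenia, then first thrombocytopenia: 4-3-3
- grade 3 rash, then first cytopenia: 4-3-3
- two neutropenias, then first thrombocytopenia: 4-3-2-3, read literally

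A subject at 3 mg because of an earlier *platelet* drop is not affected. That subject falls under the additional-drop row and goes to 2 mg.

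**3. Carfilzomib at the same event.** In this band the platelet event leaves the dose where it was, but where it was depends on the route (Table 7-1, Table 7-2, Section 7.1.1.1.4):
- Prior rash, or a febrile first neutropenia with ANC 0.5 to 0.75 x 10^9/L: 56 to 56 mg/m2, if nothing else has reduced it.
- One prior neutropenia with ANC < 0.5 x 10^9/L: carfilzomib has already gone from 56 to 45, so 45 to 45, unless re-escalated after a tolerated cycle (7.4.1.1).
- The 4-3-2-3 path: a second neutropenia counts only below 500 per µL, so at least one decrement has occurred. The dose is 45, or 36 if both episodes were below 0.5, again unless re-escalated.
- Baseline hepatic impairment: start at 42, so 42 to 42, unless re-escalated.

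**4. Where the gap is covered.** With platelets < 10 x 10^9/L or bleeding, carfilzomib falls one level. For a first neutropenia with ANC < 0.5 x 10^9/L at 3 mg, pomalidomide stays at 63 mg per course, but carfilzomib falls one level (from 56 to 45 mg/m2, (56 − 45)/56 = 20%) and growth factor is given.

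**5. A smaller second band.** Fever with ANC 0.5 to < 1.0 x 10^9/L also triggers the first-episode neutropenia row. Table 7-2 keeps carfilzomib at full dose at 0.5 to 0.75 and has no row from 0.75 to < 1.0. For a grade 3 or 4 infection with ANC < 1.0, Table 7-3 holds carfilzomib and then says to "follow hematologic toxicities dose reduction guidelines", which leads back to Table 7-2. A subject at 3 mg gets no dose step here either, but does get growth factor.

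**The case against.** The strongest reply is that the protocol already allows a lower restart. Table 7-5 is headed as guidance with recommended actions, modification rests on the investigator's opinion, and Table 7-4 provides 2 mg and 1 mg levels. Read against a 4 mg nominal dose, 3 mg is simply the first decrement, and few investigators would raise pomalidomide from 2 to 3 mg after a thrombocytopenia. Section 7.1.1.2.1 refers to the pomalidomide label for more detail, which cannot be checked here. Table 7-4 also has a footnote marker on the nominal dose whose text is not visible, and it might address reduced starts. The hepatic route is narrow in any case, because exclusions 215 and 234 remove known cirrhosis and the larger liver-test abnormalities.

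Most of this stands as a limit on size, but it does not remove the point. Discretion permits a lower restart; the visible text does not direct one, and for these subjects it prints a specific dose that is not a reduction. The SAP (6.5) also excludes from the per-protocol set subjects with a deviation coded as pomalidomide not given per protocol. The code's detailed definition is not in the documents, but a site that chooses 2 mg where the table prints 3 mg should not have to wonder about it.

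A reader might infer three stronger things:
- *That carfilzomib stays at 56 mg/m2 in all these cases.* It need not. On several routes it is already 45, 36 or 42, so both drugs may have been reduced before the platelet event. The point concerns only the absence of a further reduction for that event.
- *That the protocol intends a rise from 2 to 3 mg.* The relative rule for additional drops points the other way, and no visible text provides for pomalidomide re-escalation. The rise is a literal consequence of the row, not a stated aim.
- *That subjects are left unprotected.* Both drugs are held, blood counts are weekly, and pomalidomide waits for platelets above 50 x 10^9/L. Only the restart dose is in question.

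**Conclusion.** Wrong as written, minor. In both first-episode rows of Table 7-5 the fixed 3 mg gives no reduction to a subject already at 3 mg. For a first non-bleeding platelet drop to 10 to < 25 x 10^9/L, Table 7-2 adds no carfilzomib reduction. For that event pomalidomide stays at 63 mg per course, where a subject coming from 4 mg would have had a 25% cut.

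The conclusion assumes that the neutropenia and thrombocytopenia blocks count their first episodes separately, as the table is laid out, and that neither the unseen Table 7-4 footnote nor the label resolves the case. At most the 52 subjects who received carfilzomib could be affected. The documents do not say how many are still on pomalidomide, or how many of those are at 3 mg or less, so no frequency can be given. No efficacy hypothesis test depends on it.

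**What to change.** In both first-episode rows of Table 7-5, replace the fixed dose with a restart 1 mg below the dose before the interruption, noting in brackets that this is 3 mg for a subject who was at 4 mg. Add one line for a subject already at 1 mg, where Table 7-4 has no lower level, for example to discontinue pomalidomide. The 4 mg case is unchanged; 3 mg becomes 2 mg and 2 mg becomes 1 mg.

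The cost is two edited rows, one added line and a clarification to sites with subjects still on pomalidomide. Amendment 4 already revised the pomalidomide guidance for nonhematologic toxicity, so this is an edit of a familiar kind. No new data are collected and no analysis changes.
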